## 5.2 Interim Analyses

The following analyses are planned:

- Informal interim analysis after study completion of approximately 30 subjects (Phase I) to assure that the data structure is robust for data analyses; no decisions pertaining to enrollment will be made based on findings of this interim analysis.
- Informal interim analysis after study completion of approximately 100 subjects (30 Phase I + 70 Phase II) to finalize endpoint programs and validate them for end of study data analysis; no decisions pertaining to enrollment will be made based on findings of this interim analysis.
- Formal final analysis after study completion of all subjects (30 Phase I + 220 Phase II).

## 5.3 Subgroup Analyses

Subgroup Analyses will be performed in the following subgroups:

- gender (male, female)

No adjustments for multiple comparisons will be made. Additional analyses may be performed as appropriate.

## 5.4 Justification of Pooling

Poolability of subjects from study sites will be based on the fact that each site follows the identical clinical protocol. At the end of the study, to justify pooling data across sites, the

Boston Scientific

Statistical Analysis Plan - Randomized Evaluation of PCLs Using Three EUS-FNA Needles

90912872 Rev/Ver AA

Page 21 of 24

comparability of baseline variables and demographic characteristics will be assessed across sites. Baseline demographic characteristics include age and gender. Also, the effect of study site will be investigated to determine the poolability of primary endpoint from different sites. If low enrolling sites exist (fewer than 5 subjects per site for example), they may be combined into one 'center' for purposes of poolability analysis. An analysis of variance will be used for the primary endpoint to assess differences between study centers. Each test will be done at a 5% significance level, with no adjustment for multiplicity of variables. If a significant difference is found among centers, then multiple comparisons of centers will be done with an overall significance level of at most 5%, to identify any sites significantly different from the rest. Subsequently, at the end of the study, the primary endpoint will be analyzed both with and without these sites.

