8.2.4. Randomization

Enrolled patients will be assigned to the 19G Flex, 22 G or 19 G Arm in a 2:1:1 ratio by randomization schedules which will be computer-generated using a pseudo-random number generator. An Interactive Web Response System (IWRS) will be utilized.

Randomization will be stratified (block randomization) by the following strata:

- Investigational center
- PCL location: head/uncinate, other

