12 AUG 2016

FINAL

Boston Scientific
 Randomized Evaluation of PCLs Using Three EUS-FNA Needles
 90869947 Rev/Ver. AG
 Page 25 of 46

Exclusion criteria #1 may be documented after a patient was randomized and the EUS procedure was started. In such cases, the patient will be excluded from the study and no longer be a part of the ITT cohort.

The Modified Intent-to-treat population will consist of ITT population with salvage, namely the patients with 19G + Salvage, 22G + Salvage, and 19G Flex+ Salvage.

The per-protocol (PP) cohort will consist of the subset of the ITT patients in whom the target lesion could be reached and EUS-FNA yielded any aspirate, used the assigned needle, and there were no major protocol deviations. All endpoints will be analyzed for the ITT and PP study populations, for all patients and stratified by EUS-FNA needle type (by randomization arm).

Justification for pooling of data from all study sites will be assessed using standard poolability tests.

Multivariate analyses will be carried out to assess potential correlations between the primary endpoint and PCL location, PCL size, route of access (duodenal, esophageal, or gastric), needle used, and number of locules.

The following analyses are planned:

- Informal interim analysis after study completion of approximately 30 subjects (Phase I) to assure that the data structure is robust for data analyses; no decisions pertaining to enrollment will be made based on findings of this interim analysis.
- Informal interim analysis after study completion of approximately 100 subjects (30 Phase I + 70 Phase II) to finalize endpoint programs and validate them for end of study data analysis; no decisions pertaining to enrollment will be made based on findings of this interim analysis.
- Formal final analysis after study completion of all subjects (30 Phase I + 220 Phase II).

A statistical analysis plan will be in place prior to enrollment. Changes to the plan or additional analyses conducted will be identified as *ad hoc* analyses.

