## 5.5 Multivariable Analyses

Multivariate analyses will be carried out to assess potential correlations between the primary endpoint and PCL location, PCL size, route of access (duodenal, esophageal or gastric), needle used, and number of locules. To analyze the salvage cross-over rate, the mixed model multivariate analysis approach above or any other suitable analysis approach will be adopted. Other multivariate analysis (e.g. impact of different predictors to salvage or not) will be done (if necessary) to address any clinical need.

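### The pooling check in SAP 5.4 looks at centre means and never estimates whether the needle effect varies between centres, so its flags can mislead in both directions

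*SAP*

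**What the plan says.** Protocol 9.3 is general: "Justification for pooling of data from all study sites will be assessed using standard poolability tests". It names no test.

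SAP 5.4 gives the detail. Pooling rests first on all sites following one protocol and on comparable baseline variables across sites. For the outcome, "the effect of study site will be investigated to determine the poolability of primary endpoint from different sites", and the tool is stated: "An analysis of variance will be used for the primary endpoint to assess differences between study centers". On the level, "Each test will be done at a 5% significance level, with no adjustment for multiplicity of variables". A significant result leads to comparisons among centres "to identify any sites significantly different from the rest", after which "the primary endpoint will be analyzed both with and without these sites". Sites with few patients (the example is fewer than 5) may be combined.

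Two other places bear on the point. Protocol 8.2.4 lists "Investigational center" as a randomisation stratum, beside lesion location (SAP 4.5 mentions only location). The multivariable analysis in SAP 5.5 covers "PCL location, PCL size, route of access (duodenal, esophageal or gastric), needle used, and number of locules", so needle is listed but centre and needle-by-centre are not. The only subgroup named in SAP 5.3 is gender.

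**The concern.** The trial compares needles. Pooling centres for that comparison is questionable if the difference between needles depends on who uses them. It is not questionable merely because one centre sees larger or more viscous cysts and aspirates less with every needle. With allocation balanced within centre, such a shift cancels from each needle contrast.

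Every step of the SAP 5.4 rule concerns the centre's overall mean. Two misreadings can follow. Ordinary case-mix may be reported as a pooling problem, beside a second primary result that leaves out sites selected on their outcome. Or centres may look alike on average, and be called poolable, while the needle advantage is large at some and absent at others. The variation between operators that a reader would want to see is not reported anywhere.

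**Working it through.** **Plan's own figure.** The documents give no operating characteristics for the pooling test. As a check that the design inputs are read correctly, the stated conjunctive power of 0.901 (SAP 3.1.2: means 77/77/67, SDs 4.67/4.67/15.29, n = 50/25/25, one-sided 0.05, Hochberg) comes out at 0.904 with a Welch t reference.

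**Inputs from the documents.** 250 patients, 7 to 12 centres, 2:1:1 allocation, means 77 (both 19 G needles) and 67 (22 G), SD 15.29.

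**Assumptions.** 8 or 12 equal centres, normal outcomes, a common SD of 15.29 unless stated, and the sizes of the centre shifts and effect differences. Tests are at 5%.

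**Case 1: centre shift only.** Half the centres are 5 points up and half 5 points down, with a needle effect of 10 points everywhere.
- Residual variance of a one-way centre ANOVA: 15.29² + 10² × 0.75 × 0.25 = 233.8 + 18.75 = 252.5.
- Noncentrality: 250 × 5² / 252.5 = 24.7.
- Power of the centre F-test: about 97% with 8 centres (7 and 242 df) and 94% with 12 (11 and 238 df). Simulation gives 97% and 93%.

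The arm-by-centre test rejects in 4% to 5%, its nominal level.

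**Case 2: needle effect varies, centre means equal.** The effect is 20 points in half the centres and 0 in the rest. Under 2:1:1 the means stay equal if 22 G moves by ∓7.5 and both 19 G needles by ±2.5, since 0.25 × 7.5 = 0.75 × 2.5.
- Between-centre signal: zero by construction.
- Interaction noncentrality: 250 × (0.25 × 7.5² + 0.75 × 2.5²) / 233.8 = 250 × 18.75 / 233.8 = 20.1.

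**Cases 3 and 4: same 20/0 effect without cancellation.** Either only 22 G varies, or only the two 19 G needles vary.

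Simulated share of trials flagged (4,000 per row, common SD 15.29; 8 centres / 12 centres):

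| Case | Centre ANOVA | Arm-by-centre test |
|---|---|---|
| 1. Shift ±5, same needle effect | 97% / 93% | 5% / 4% |
| 2. Effect 20/0, centre means equal | 2% / 2% | 82% / 69% |
| 3. Effect 20/0, only 22 G varies | 31% / 18% | 83% / 70% |
| 4. Effect 20/0, only 19 G needles vary | 100% / 100% | 82% / 69% |

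Cases 1 and 4 give nearly the same signal from the centre ANOVA, although one is harmless to the comparison and the other is not.

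**The protocol's own operator figures.** Protocol Figure 4 lists six investigators' expected mean ratios. The 19 G minus 22 G differences are 30, 20, 0, 0, 40 and 20 points. A centre's mean under 2:1:1 is 0.75 × (19 G value) + 0.25 × (22 G value):
- Investigator 3: 0.75 × 80 + 0.25 × 80 = 80, effect 0.
- Investigator 5: 0.75 × 90 + 0.25 × 50 = 80, effect 40.
- Investigator 6: 0.75 × 85 + 0.25 × 65 = 80, effect 20.
- Investigator 2: 0.75 × 90 + 0.25 × 70 = 85, effect 20.

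Investigators 3, 5 and 6 share one centre mean with very different effects. Investigators 2 and 6 share one effect with different centre means.

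**Check of the remedy.** With the plan's unequal SDs (4.67 and 15.29) and no interaction at all, an ordinary arm-by-centre F-test rejects in 26% of trials with 8 centres and 38% with 12. It needs a model with arm-specific variances.

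**The case against.** Four points can be made for the plan.

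1. *The centre ANOVA often reacts to varying needle effects.* This stands. The 2% result needs changes that cancel exactly. If only the 19 G needles vary, the check flags nearly always. With all six Figure 4 investigators as centres (240 patients, 6 or 12 equal centres), centre means run from 72.5 to 90 and the check flags roughly 96% and 82% at SD 15.29, against 99.7% and 98% for the interaction test. A reader might infer that the check is blind to operator-dependent effects. The documents do not support that. It can miss them, and it cannot identify them.

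2. *No data are lost.* This stands. A reader might take the rule to remove sites from the primary analysis, but SAP 5.4 keeps the full analysis and adds a second. Type I error and sample size are untouched.

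3. *The ANOVA model is not written out, and standard tests could include an interaction.* This stands in part. No interaction is ruled out, but the stated target is the effect of site, and the follow-up looks for outlying sites.

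4. *An interaction test is no clean replacement.* This stands. The ordinary version over-rejects under the plan's SDs. Power is also limited: 250/8 and 250/12 give about 31 and 21 patients per centre, so about 8 and 5 per standard-needle arm.

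**Conclusion.** The point holds as one of interpretation. SAP 5.4 bases its outcome check for pooling on centre means, which do not threaten a comparison randomised within centre. Neither document estimates variation of the needle effect between centres, which does.

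At common SD 15.29 with 8 or 12 equal centres, ±5-point case-mix is flagged in about 93% to 97% of trials. A 20-versus-0-point needle effect with equal centre means is flagged in about 2%, a constructed extreme. Between these cases the flag rate depends on which needle varies (18% to 100% in the cases tried), and the flag does not say why.

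The shifts, the equal centre sizes and normality are assumptions; the documents give no between-centre SD. The 15.29 comes from the spread of six investigators' estimates, so the patient-level SD may be larger. A separate run (10 centres of 24, centre means varying with an assumed SD of 10 points, same needle effect everywhere) still flags 92% at patient SD 25 and 76% at SD 35. The contrast with an interaction test's roughly 5% therefore does not depend on the smaller SD.

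The change is worth making because it is cheap and replaces a stated rule whose flags can be misread. It does not call the primary test into question.

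**What to change.** In SAP 5.4:

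- Report both needle contrasts (19 G Flex versus 22 G, and 19 G versus 22 G) by centre with confidence intervals in a forest plot. Combine small centres until each has patients in every arm. The fewer-than-5 example is not enough: under simple 2:1:1 allocation a five-patient centre has no 22 G patient with probability 0.75⁵ = 24% (block size is not stated).
- Add an arm-by-centre term from a model with arm-specific variances. Read it as an estimate of heterogeneity, not as a pass/fail gate.
- Replace the with-and-without analysis of outcome-selected sites by a leave-one-centre-out sensitivity analysis.
- Keep centre means as description.

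The cost is SAP wording, one model and one plot, with no new data and no change in sample size. The limitation to state is low power for interaction, given the few standard-needle patients per centre.

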## 5.5 Multivariable Analyses

Multivariate analyses will be carried out to assess potential correlations between the primary endpoint and PCL location, PCL size, route of access (duodenal, esophageal or gastric), needle used, and number of locules. To analyze the salvage cross-over rate, the mixed model multivariate analysis approach above or any other suitable analysis approach will be adopted. Other multivariate analysis (e.g. impact of different predictors to salvage or not) will be done (if necessary) to address any clinical need.

## 5.6 Other Analyses

### 5.6.1 Baseline Characteristics

Baseline data will be summarized overall and for each needle to assess subject demographics, clinical history and pre-procedure characteristics. Data will be summarized using descriptive statistics for continuous variables (mean, standard deviation, number of observations, minimum and maximum) and frequency statistics (percent of conformers, number of conformers, number of observations) for discrete variables.

### 5.6.2 Post-Procedure Endpoints

Post-procedure information will be collected as detailed in the clinical trial schedule in the protocol. Data will be summarized overall and for each needle using descriptive statistics for continuous variables (mean, standard deviation, number of observations, minimum and maximum) and frequency statistics (percent of conformers, number of conformers, number of observations) for discrete variables.

### 5.6.3 Subject Disposition

Subject disposition (e.g., number completing the study, number lost-to-follow-up) will be summarized overall and for each needle with frequency tables.

### 5.6.4 Time-to-Event Methods

The Kaplan-Meier product-limit method will be used to estimate event rates for time-to-event endpoints. Kaplan-Meier plots of time-to-event endpoints will be constructed.

## 5.7 Changes to Planned Analyses

This statistical analysis plan has been updated prior to performing the final statistical analyses due to updates in the protocol.

## 6 VALIDATION

All clinical data reports generated per this plan will be validated per 90702587, Global WI: Clinical Data Reporting Validation.

## 7 PROGRAMMING CONSIDERATIONS

### 7.1 Statistical Software

All statistical analyses will be done using The SAS System software, version 8 or higher (Copyright © 2000 SAS Institute Inc., [name], USA. All rights reserved).

### 7.2 Format of Output

Results of analysis will be output programmatically to Word documents from SAS with no manual intervention. All output for the final statistical report will be in the form of a Word document containing tables, figures, graphs, and listings, as appropriate.

### 7.3 Rules and definitions for calculated variables

Rules for programming will be documented accordingly in the SAS code or in the specific table or listing footnotes. This may include references to CRF pages, manipulation of variables, or other appropriate identifiers

## 8 APPENDIX
